### 7.2.2.1 Dose Modifications for Lenvatinib Management of Hypertension

Hypertension is a recognized side effect of treatment with drugs inhibiting VEGF signaling.

Investigators should therefore ensure that participants enrolled to receive treatment with lenvatinib have blood pressure (BP) of  $\leq 150/90$  mm Hg at the time of study entry and, if known to be hypertensive, have been on a stable dose of antihypertensive therapy for at least 1 week before Cycle 1/Day 1. Early detection and effective management of hypertension are important to minimize the need for lenvatinib dose interruptions and reductions.

Regular assessment of BP should be conducted as detailed in the Schedule of Activities and in Section 9.5.2. Hypertension will be graded using CTCAE v4.0, based on BP measurements only (and not on the number of antihypertensive medications). Management of lenvatinib administration will be based on the grade of hypertension according to [Table 8](#) in the Dose Modification Guidelines.

If the participant's initial BP measurement is elevated (systolic BP  $\geq 140$  mmHg or diastolic BP  $\geq 90$  mmHg), the BP measurement should be repeated at least 5 minutes later. The mean value of 2 measurements at least 5 minutes apart is defined as one BP assessment. If the BP

assessment (ie, the mean of the 2 BP measurements obtained at least 5 minutes apart) is elevated (systolic BP  $\geq 140$  mm Hg or diastolic BP  $\geq 90$  mmHg), a confirmatory assessment should be obtained at least 30 minutes later by performing 2 measurements (at least 5 minutes apart) to yield a mean value.

Antihypertensive agents should be started as soon as elevated BP (systolic BP  $\geq 140$  mm Hg or diastolic BP  $\geq 90$  mm Hg) is confirmed on 2 assessments at least 30 minutes later. One BP assessment is defined as the mean value of 2 measurements at least 5 minutes apart. The choice of antihypertensive treatment should be individualized to the participant's clinical circumstances and follow standard medical practice. For previously normotensive participants, appropriate antihypertensive therapy should be started when systolic BP  $\geq 140$  mm Hg or diastolic BP  $\geq 90$  mm Hg is first observed on 2 assessments at least 30 minutes apart. For those participants already on antihypertensive medication, treatment modification may be necessary if hypertension persists.

Lenvatinib should be withheld in any instance where a participant is at imminent risk to develop a hypertensive crisis or has significant risk factors for severe complications of uncontrolled hypertension (eg, BP  $\geq 160/100$  mm Hg, significant risk factors for cardiac disease, intracerebral hemorrhage, or other significant co-morbidities). Once the participant has been on the same antihypertensive medications for at least 48 hours and the BP is controlled, lenvatinib should be resumed as described below.

Participants who have had systolic BP  $\geq 160$  mm Hg or diastolic BP  $\geq 100$  mm Hg must have their BP monitored on Day 15 (or more frequently as clinically indicated) until systolic BP has been  $\leq 150$  mm Hg and diastolic BP has been  $\leq 95$  mm Hg for 2 consecutive treatment cycles. If a repeat event of systolic BP  $\geq 160$  mm Hg or diastolic BP  $\geq 100$  mm Hg occurs, the participant must resume the Day 15 evaluation until systolic BP has been  $\leq 150$  mm Hg and diastolic BP has been  $\leq 95$  mm Hg for 2 consecutive treatment cycles.

Under exceptional circumstances, participants will have the option of having BP measured between visits obtained locally by a health care professional. A BP log will be provided to capture the blood pressure evaluations between study visits. The health care professional will provide documentation of the BP measurement to the study-site.

The following guidelines should be followed for the management of systolic BP  $\geq 160$  mmHg or diastolic BP  $\geq 100$  mmHg confirmed on 2 measurements after at least 30 minutes:

1. Continue study drug and institute antihypertensive therapy for participants not already receiving this.
2. For those participants already on antihypertensive medication, the dose of the current agent may be increased, if appropriate, or 1 or more agents of a different class of antihypertensive should be added. Study treatment can be continued without dose modification.

3. If systolic BP  $\geq 160$  mmHg or diastolic BP  $\geq 100$  mmHg persists despite maximal antihypertensive therapy, then lenvatinib administration should be interrupted and restarted at 1 dose level reduction only when systolic BP  $\leq 150$  mmHg and diastolic BP  $\leq 95$  mmHg and the participant has been on a stable dose of antihypertensive medication for at least 48 hours.
- If systolic BP  $\geq 160$  mmHg or diastolic BP  $\geq 100$  mmHg recurs on the first dose reduction despite optimal management of hypertension with antihypertensive medications (either by dose increase or the addition of a different class of antihypertensive), then lenvatinib administration should be interrupted and restarted at an additional dose reduction only when systolic BP  $\leq 150$  mmHg and diastolic BP  $\leq 95$  mmHg and the participant has been on a stable dose of antihypertensive medication for at least 48 hours.
- If systolic BP  $\geq 160$  mmHg or diastolic BP  $\geq 100$  mmHg recurs on the second dose reduction despite optimal management of hypertension with antihypertensive medications (either by dose increase or the addition of a different class of antihypertensive), then lenvatinib administration should be interrupted and restarted at a third dose reduction dose only when systolic BP  $\leq 150$  mmHg and diastolic BP  $\leq 95$  mmHg and the participant has been on a stable dose of antihypertensive medication for at least 48 hours.
- Additional dose reduction should be discussed with the sponsor.

The following guidelines should be followed for the management of Grade 4 hypertension (life threatening consequences):

1. Institute appropriate medical management
2. Discontinue study drug.

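### Section 7.2.2.1 gives a blood pressure of 160/100 mm Hg or more as an example for withholding lenvatinib, and also as the trigger for guidance that starts by continuing it

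*Combined protocol and SAP*

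**What the plan says.** Three pieces of text in the protocol bear on this.

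- **The withholding paragraph, midway through Section 7.2.2.1.** "Lenvatinib should be withheld in any instance where a participant is at imminent risk to develop a hypertensive crisis", or where the participant "has significant risk factors for severe complications of uncontrolled hypertension (eg, BP" being the first item in the bracketed list, at 160/100 mm Hg or more. Cardiac risk factors, intracerebral hemorrhage and other significant comorbidities follow as further items. Lenvatinib is resumed as set out later in the section, once pressure is controlled and antihypertensive medication has been unchanged for at least 48 hours.
- **The numbered guidance later in the same section.** It applies to systolic pressure of 160 mmHg or more, or diastolic of 100 mmHg or more, confirmed on 2 measurements after at least 30 minutes. Step 1: "Continue study drug and institute antihypertensive therapy for participants not already receiving this". Step 2, for those already treated, intensifies the antihypertensive regimen and adds: "Study treatment can be continued without dose modification". Step 3 is the first to stop the drug: if the level "persists despite maximal antihypertensive therapy, then lenvatinib administration should be interrupted and restarted at 1 dose level reduction only when" pressure is at or below 150 systolic and 95 diastolic on a stable regimen.
- **Table 8 in Section 7.2.2.** Grade 3 hypertension leads to a hold and a restart at reduced dose. Footnote a limits that row to Grade 3 that remains despite optimal antihypertensive therapy.

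**The concern.** The same two numbers, 160 and 100, lead to opposite first actions. The withholding paragraph makes the reading itself an example of the condition for stopping. The numbered steps make it a reason to treat the pressure and carry on. Nothing in the section says which text prevails.

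Two sites seeing the same participant could therefore do different things and both point to the protocol. The first stake is participant safety, in an arm where the protocol itself names hypertension as a known risk of the drug. The second is dose delivered. The restarts described after the withholding paragraph are at a reduced dose, and Section 7.2.2 does not allow a reduced dose to be raised again except after a mistaken reduction. On that reading, one site continues at full dose while the other holds and then reduces for good. Section 10.11 also promises to report deviations from protocol-directed administration. In the conflict cases there is no single directed action against which to judge a deviation.

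**Working it through.** No sample size, error rate or event count enters this point, so the check is a comparison of text.

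**Conditions attached to each instruction**

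| | Withholding paragraph | Numbered steps | Table 8, Grade 3 row |
|---|---|---|---|
| Level | 160/100 or more; 'and' or 'or' not stated | systolic 160 or more, or diastolic 100 or more | CTCAE grade |
| Confirmation | none stated | 2 measurements after at least 30 minutes | none stated in the row |
| Failure of therapy required | no | only for interruption (step 3, maximal therapy) | yes (footnote a, optimal therapy) |
| Other risk factor required | not stated; the pressure is a list item of its own | no | no |
| First action | withhold | continue | hold |

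**Applying them to cases** (readings chosen for illustration)

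1. *Confirmed 165/105, no antihypertensive.* 165 ≥ 160 and 105 ≥ 100, so the withholding example is met however the slash is read. The numbered trigger is also met, and step 1 says continue. The instructions are opposed.
2. *Confirmed 165/105, on antihypertensives but not maximal therapy.* The withholding example is met. Step 2 allows continuation at an unchanged dose. The instructions are opposed in effect, although step 2 is permissive.
3. *Confirmed 165/105, persisting on maximal therapy.* Step 3 interrupts, in line with the withholding paragraph. There is no conflict on whether to stop.
4. *Confirmed 165/95.* The numbered trigger is met because it uses 'or'. The withholding example is met only if 160/100 also means 'or'. Whether there is a conflict depends on an unstated point.
5. *Single unconfirmed 165/105.* The withholding example carries no confirmation step. The numbered guidance is not yet triggered. The texts differ in timing, but the numbered steps do not yet say continue.

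Cases 1 and 2 are the certain conflict: both limits exceeded, confirmed, and therapy not yet maximal.

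**Does another passage break the tie?** Section 7.2.2 sends the investigator to the subsections, including 7.2.2.1, before Table 8. Section 7.2.2.1 in turn says lenvatinib management follows the grade in Table 8. Each refers to the other. Footnote a agrees with step 3 in tying the hold to failure of therapy, but it neither mentions the withholding paragraph nor limits it.

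**The case against.** The best defence is that the withholding paragraph was written for a high-risk subset. Its wording concerns severe complications of hypertension that is uncontrolled, and it opens with imminent crisis. Its 48-hour condition for resuming is the same as in step 3. Both step 3 and footnote a reserve interruption for pressure that stays high despite full therapy. Read this way, the numbered steps cover the ordinary participant, the paragraph covers the exceptional one, and the problem is unclear scope.

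That reading is plausible and may well be the intent, but it is not what the text says. The pressure value is listed as an example of a significant risk factor in its own right, beside cardiac risk and intracerebral hemorrhage. No words require it to occur together with them or after therapy has failed. If the subset reading is intended, stating it is the correction needed.

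The defence is right that the triggers are not identical. Confirmation and 'or' appear only in the numbered guidance, so it would go too far to say that the texts conflict at every reading of this size. Cases 3 to 5 above show where they do not, or where it cannot be told.

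**Conclusion.** The inconsistency stands as a contradiction in a stated clinical-management rule. It is certain when systolic is 160 or more and diastolic is 100 or more, confirmed, in a participant not yet on maximal antihypertensive therapy. It affects participant safety, dose interruptions and exposure in the lenvatinib arm. It should be corrected. Because lenvatinib may continue alone after 35 pembrolizumab infusions, it applies to anyone still taking the drug.

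Three stronger inferences are not supported.

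- *That it directly shifts the safety endpoint of discontinuations due to adverse events.* Neither instruction discontinues the drug: one holds and then resumes, the other continues. In the hypertension guidance, discontinuation belongs to Grade 4. A hold could lead to discontinuation only indirectly, for example through the rule in Section 8.1 on interruptions of more than 28 days.
- *That a number of affected participants can be given.* Equal thirds of the planned groups would put 3 × 66/3 + 90/3 = 96 participants on lenvatinib. The per-arm caps allow up to about 3 × 25 + 40 = 115. Arms may close for futility from about 10 participants per group, or 4 × 10 = 40. The documents give no rate of reaching this pressure, and not everyone who reaches it meets both instructions.
- *That it bears on the response-rate analysis.* It does not change the sample size or the error rates of that analysis.

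**What to change.** The sponsor should reconcile the withholding paragraph, steps 1 to 3 and Table 8 with footnote a, so that one stated pressure and risk condition leads to one action. The revised text should say:

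- whether the pressure example applies alone or only with other listed risk factors;
- whether a confirmed reading is needed before withholding;
- whether 160/100 means both limits or either;
- which text prevails if more than one applies.

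Which threshold and which action to adopt is for the sponsor to decide. The cost is rewording one paragraph, with matching cross-references, in a protocol amendment. No assessment, sample size or analysis changes.

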#### **7.2.2.2 Dose Modifications for Lenvatinib Management of Proteinuria**

Regular assessment of proteinuria should be conducted as detailed in the SoA in Section 2. Guidelines for assessment and management of proteinuria are as follows:

##### **Detection and Confirmation**

1. Perform urine dipstick testing per the SoA in Section 2
2. A 24-hour urine collection (initiated as soon as possible and at least within 72 hours) or an immediate spot urine protein-to-creatinine ratio (UPCR) test is required in the following situations:
  - The first (initial) occurrence of  $\geq 2+$  proteinuria on urine dipstick while on study drug
  - A subsequent increase in severity of urine dipstick proteinuria occurring on the same lenvatinib dose level
  - When there has been a lenvatinib dose reduction and at the new dose level the urine protein dipstick result is  $\geq 2+$

3. A 24-hour urine collection (initiated as soon as possible and at least within 72 hours) to verify the grade of proteinuria is required when UPCR is  $\geq 2.4$ .

### **Grading of Proteinuria**

- Grading according to NCI CTCAE v4.0 will be based on the 24-hour urinary protein result if one has been obtained. Management of lenvatinib administration will be based on the grade of proteinuria according to [Table 8](#).

### **Monitoring**

- Urine dipstick testing for participants with proteinuria  $\geq 2+$  should be performed on Day 15 (or more frequently as clinically indicated) until the results have been 1+ or negative for 2 consecutive treatment cycles.
- Proteinuria monitoring can be performed at the local laboratory or investigator site but must be managed by the site physician.
- In the event of nephrotic syndrome, lenvatinib must be discontinued

#### **7.2.2.3 Dose Modifications for Lenvatinib Management of Diarrhea**

Instructions in [Table 8](#) should be followed for the management of diarrhea. An anti-diarrheal agent should be recommended to the participant at the start of study treatment and participants should be instructed and educated to initiate anti-diarrheal treatment at the first onset of soft bowel movements. The choice of anti-diarrheal agent should be individualized to the participant's clinical circumstances and follow standard medical practice. If signs/symptoms of diarrhea persist despite optimal medical management, instructions contained in [Table 8](#) should be followed.

#### **7.2.2.4 Dose Modifications for Lenvatinib Management of Hepatotoxicity**

Regular monitoring of liver function tests (eg, alanine transaminase [ALT], aspartate transaminase [AST], bilirubin levels) should be conducted as detailed in the SoA in Section 2. If signs/symptoms indicating liver injury occur, instructions contained in [Table 8](#) should be followed. Appropriate supportive care should be provided together with close monitoring. If hepatic failure occurs, lenvatinib must be discontinued.

#### **7.2.2.5 Dose Modifications for Lenvatinib Management of Thromboembolic Events**

Participants should be advised to pay attention to the symptoms suggestive of venous thromboembolic events, which include acute onset of shortness of breath, dyspnea, chest pain, cough, hemoptysis, tachypnea, tachycardia, cyanosis, and deep vein thrombosis (DVT) signs including lower-extremity swelling, redness, and warmth to touch or tenderness. Participants should be instructed to report any of these signs and symptoms promptly to the treating physician. If a thromboembolic event is confirmed, instructions contained in [Table 8](#) should be followed. Appropriate supportive care should be provided together with close monitoring. If a participant experiences life-threatening (Grade 4) thromboembolic reactions, including pulmonary embolism, the study treatment must be discontinued.

Arterial thromboembolic events (eg, new onset, worsening, or unstable angina, myocardial infarction, transient ischemic attack, and cerebrovascular accident) of any grade require study treatment discontinuation.

#### **7.2.2.6 Dose Modifications for Lenvatinib Management of Posterior Reversible Encephalopathy Syndrome (PRES)**

Posterior reversible encephalopathy syndrome/Reversible Encephalopathy Syndrome/Reversible Posterior Leukoencephalopathy Syndrome (PRES/RPLS) is a neurological disorder that can present with headache, seizure, lethargy, confusion, altered mental function, blindness, and other visual or neurological disturbances. Mild to severe hypertension may be present. A magnetic resonance imaging (MRI) is necessary to confirm the diagnosis of PRES. Appropriate measures should be taken to control blood pressure. In participants with signs or symptoms of PRES, instructions in [Table 8](#) should be followed.

#### **7.2.2.7 Dose Modifications for Lenvatinib Management of Hypocalcemia**

Serum calcium should be monitored Q3W as detailed in the SoA in Section 2. Corrected serum calcium should be used to assess the grade of hypocalcemia per CTCAE v 4.0, using the following formula:

$$\text{Corrected calcium} = ([4 - \text{serum albumin in g/dL}] \times 0.8 + \text{serum calcium})$$

The formula is not applicable when serum albumin concentration is normal ( $>4$  g/dL); in such situations, the total (uncorrected) serum calcium should be used instead. Hypocalcemia should be treated per institutional guidelines (eg, using, as appropriate, calcium, magnesium, and vitamin D supplementation) until resolution.

#### **7.2.2.8 Dose Modifications for Lenvatinib Management of Hemorrhage**

Instructions in [Table 8](#) should be followed for the management of hemorrhage. Either resume at a reduced dose or discontinue lenvatinib depending on the severity and persistence of hemorrhage.

#### **7.2.2.9 Management of Gastrointestinal Perforation or Fistula Formation**

Lenvatinib should be discontinued in any participants who develop gastrointestinal perforation of any grade or  $\geq$ Grade 3 fistula.

#### **7.2.2.10 Management of Osteonecrosis of the Jaw**

Perform an oral examination prior to treatment with lenvatinib and periodically during lenvatinib treatment. Advise participants regarding good oral hygiene practices. Avoid invasive dental procedures, if possible, while on lenvatinib treatment, particularly in participants at higher risk. For participants requiring invasive dental procedures, discontinuation of bisphosphonate treatment may reduce the risk of ONJ. Withhold lenvatinib if ONJ develops and restart based on clinical judgement of adequate resolution.

#### **7.2.2.11 Dose Modifications for Overlapping Toxicities**

Based on the known toxicity profiles of pembrolizumab and lenvatinib, certain treatment-related AEs are uniquely associated with one drug versus the other. For example,

hypertension, arterial thrombotic events, proteinuria, and hemorrhagic events are known risks for lenvatinib treatment, while immune-related AEs are risks for pembrolizumab treatment. However, certain AEs, such as such as diarrhea, hypothyroidism, and liver enzyme elevation, may be initially considered attributable to either study drug. Therefore, evaluation of attribution is important for determining the study drug most likely related to the AE, or an alternative etiology, and subsequently proper clinical management. The following aspects should be considered:

1. Timing of AE onset

Since lenvatinib is dosed daily and continuously due to a relatively short half-life (28 hours), and pembrolizumab is dosed Q3W due to a long half-life, lenvatinib can be interrupted to assess whether an AE improves/resolves with dechallenge (ie, interruption of treatment) based on the following two scenarios:

- If an AE is identified during a treatment cycle (ie, between 2 pembrolizumab doses), only lenvatinib dose interruption is needed.
- If an AE is identified at the beginning of a treatment cycle, lenvatinib can be interrupted and dosing of pembrolizumab should be held.

If the participant recovers from an AE in response to lenvatinib interruption (ie, positive dechallenge), the event is more likely to be related to lenvatinib. Otherwise, after excluding other alternative explanations, an immune-related AE should be considered.

2. Severity of AE

If an AE is suspected to be treatment-related and is severe/life threatening at the time of onset or is rapidly worsened, action including interrupting both drugs and initiating treatment with a corticosteroid (with exception of hypothyroidism, T1DM) and other supportive care should be taken promptly.

3. Participants receiving the combination therapy (pembrolizumab + lenvatinib) must discontinue study therapy if any of the following occur:

- 1) ALT or AST >5 X ULN for more than 2 weeks.  
Pembrolizumab will have already been permanently discontinued per [Table 6](#), but lenvatinib may be administered at a reduced dose by the time this criterion is met and must be permanently discontinued immediately.
- 2) ALT or AST >3 X ULN and (TBL >2 X ULN or INR >1.5).  
Although [Table 6](#) advises pembrolizumab to be withheld (interrupted), and [Table 8](#) advises lenvatinib to have no dose modification or a reduction, if this criterion is met, both drugs must be permanently discontinued immediately.

